9.4.2.2. Analysis of Secondary Endpoints

The key secondary endpoints which are expressed as proportions such as EASI-75, and the proportion of participants achieving a 4-point improvement from baseline in the severity of Peak Pruritus NRS measure will be analyzed using the same method as for the co-primary

endpoints. This would also apply to any other binary endpoint in the study, such as the proportion of participants with PtGA of AD of clear (0) or almost clear (1) and ≥ 2 point improvement from baseline over 12 weeks. All binary secondary endpoints are based on responder definitions and the primary analysis is estimating a composite estimand. So missing responses would be defined as “non-response” while defining the binary outcomes.

For continuous endpoints, and change from baseline in the pruritus severity and frequency using the NRS measure at all scheduled time points, a mixed-effect model with repeated measures (MMRM) will be used. This model will include the factors (fixed effects) for treatment group, disease severity group, visit, treatment-by-visit interaction, and relevant baseline value. Within the framework of MMRM, the treatment difference will be tested at the pre-specified primary time point, Week 12, as well as at the other time points by time point-specific contrasts from the MMRM model. The primary analysis of all continuous secondary endpoints is estimating a hypothetical estimand and so no imputations for missing data will be used. The MMRM methodology as mentioned above will be used under an assumption that missing data is Missing At Random (MAR).

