3.2. Secondary Endpoint(s)

3.2.1. Key Secondary Efficacy Endpoints

The key secondary efficacy endpoints are:

- Response based on ≥ 4 points improvement from baseline in the Peak Pruritus Numerical Rating Scale (NRS) from baseline at Weeks 2, 4, and 12.
- Change from baseline in Pruritus and Symptoms Assessment for Atopic Dermatitis (PSAAD) total score at Week 12.

Detailed descriptions of how the Peak Pruritus NRS and PSAAD are derived are provided in Appendix 6 and Appendix 7, respectively.

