5. GENERAL METHODOLOGY AND CONVENTIONS

5.1. Hypotheses and Decision Rules

PF-04965842 200 mg QD will be declared superior to placebo if the null hypothesis of no difference between PF-04965842 200 mg QD versus placebo for **both** co-primary endpoints is rejected at the 5% significance level. Similarly, PF-04965842 100 mg QD will be declared superior to placebo if the null hypothesis of no difference between PF-04965842 100 mg QD versus placebo for **both** co-primary endpoints is rejected at the significance level specified below.

[figure not shown]
The familywise Type-I error rate for assessing the co-primary and key secondary endpoints will be strongly controlled at 5% (2-sided) using a sequential, Bonferroni-based iterative multiple testing procedure.

The procedure will first assess the co-primary endpoints (IGA and EASI-75 at Week 12 for 200 mg QD vs placebo) at the 5% level. If this hypothesis is not rejected, then all subsequent hypotheses will not be considered statistically significant. If this hypothesis is rejected, then assessing for statistical significance will continue as follows:

- The hypothesis for severity of pruritus (Peak Pruritus NRS4) 200 mg QD vs placebo at Week 2 will be assessed at the 2.5% level. If this hypothesis is rejected, then the unused alpha level of 2.5% will be passed on to the assessment for the key secondary endpoints and the co-primary endpoints for 100 mg QD vs placebo, in the order specified in Sequence A at a 5% significance level (see figure below). All subsequent hypotheses from any point where a hypothesis cannot be rejected will not be considered statistically significant.

- If the hypothesis for severity of pruritus (Peak Pruritus NRS4) 200 mg QD vs placebo at Week 2) is not rejected at the 2.5% level, then the hypotheses for the key secondary endpoints and the co-primary endpoints for 100 mg QD vs placebo, in the order specified in Sequence A will be assessed at a 2.5% significance level (see figure below). If all hypotheses in this sequence are rejected, then the unused alpha level of 2.5% will be passed on to the assessment of the hypothesis for severity of pruritus (200 mg QD vs placebo) at Week 2 at the 5% level. All subsequent hypotheses from any point where a hypothesis cannot be rejected will not be considered statistically significant.

Figure 2. Schematic for Multiple Testing Procedure

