6.2.3. Secondary Efficacy Endpoints

6.2.3.1. Binary Endpoints

- Endpoints:
 - PP-NRS4 Response each day from Days 2-15 and Week 8;
 - Weeks 2, 4 and 8 EASI-75, IGA Response;
 - Weeks 2, 4, 8 and 12 EASI-50, EASI-90, EASI-100 Response;
 - Weeks 2, 4, 8 and 12 SCORAD50, SCORAD75;
 - Weeks 2, 4, 8 and 12 BSA <5% Response.
- Estimand strategy: Composite, Estimand 1(Section 2.1.1).
- Analysis set: FAS (Section 4). Participants must have baseline PP-NRS ≥ 4 to be included in the analysis of PP-NRS4.
- Analysis methodology: CMH and normal approximation in Section 5.2.1.
- Intercurrent events and missing data: The intercurrent event is captured through the variable definition; for participants who drop out for any reason, the response will be defined as “non-responsive” after that point.
- The number of participants, number and percent of response at each specified timepoints along with the 95% confidence interval by normal approximation will be presented for each treatment arm.
- The CMH test p-value, the estimate of the difference in proportions of response at each specified timepoints along with the corresponding 95% confidence interval by CMH normal approximation will be presented for each PF-04965842 dose group versus placebo.

6.2.3.2. Time to Achieve at Least 4 Points Improvement in the Peak Pruritus NRS from Baseline

- Analysis set: FAS (Section 4). Participants must have baseline PP-NRS ≥ 4 to be included in the analysis.
- Analysis methodology: Analyses for Time to Event Data in Section 5.2.5.

- Intercurrent events and missing data: For all participants who have not experienced the event, their time to event will be right censored at the last available measurement time.
- The number of participants, number and percent of participants censored and participants with Peak Pruritus NRS4 Response will be provided for each treatment arm.
- Estimated survival curves using the Kaplan-Meier method and number of patients at risk will be displayed graphically for each treatment arm. The 25%, 50% and 75% quartiles with their 95% confidence intervals will also be presented for each treatment arm.
- The log-rank test (stratified using baseline disease severity) p-value will be presented for each PF-04965842 dose group versus placebo.

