6.2.3.3. Continuous Endpoints

- Endpoints:
 - Weeks 2, 4, 8 and 12 Change from Baseline and Percent Change from Baseline in %BSA;
 - Weeks 2, 4, 8 and 12 Percent Change from Baseline in EASI;
 - Weeks 2, 4, 8 and 12 Change from Baseline and Percent Change from Baseline in Total SCORAD score, SCORAD subjective assessments of sleep loss (VAS);
 - Percent Change from Baseline in PP-NRS from Days 2-15, Weeks 4, 8 and 12.
- Estimand strategy: Hypothetical, Estimand 2 (Section 2.1.2).
- Analysis set: FAS (Section 4). Participants must have observed baseline measure to be included in the corresponding analysis.
- Analysis methodology: MMRM in Section 5.2.3.
- Intercurrent events and missing data: All data collected will be utilized.
- Number of participants included in the analysis will be presented for each treatment arm.
- The least square mean (LSM) of change from baseline or percentage change from baseline along with the corresponding 95% confidence interval will be presented for each treatment arm at each specified time points.

- The LSM difference along with the corresponding p-value and 95% confidence interval will be presented for each PF-04965842 dose group versus placebo arm at each specified time points.

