Appendix 2. Definition and Use of Visit Windows in Reporting

Visit windows will be used for efficacy variables, and for any safety data that display or summarize by study visit. For other endpoints (eg, ECG, vital signs), visit windows will be applied for summary statistics by study visits if required.

Visit Label	Target Day	Definition [Day window]
Baseline	Day 1 (Day of first dose)	Last observation prior to and including day of first dose
Week 2	15	Days 2 to 22
Week 4	29	Days 23 to 43
Week 8	57	Days 44 to 71
Week 12	85	Days 72 to 99
Follow Up/End of Study		
Week 16	113	Days 100 to -

For the lab values, if the calculated study day for the labelled baseline visit is not study Day 1 but falls within 28 days before the start of the study dosing, then that data should be used for the baseline instead of leaving baseline missing.

For the other values, if the calculated study day for the labelled baseline visit is not study Day 1, but falls before the start of the study dosing, then that data should be used for the baseline instead of leaving baseline missing.

If two or more visits fall into the same window, keep the one closest to the Target Day. If two visits are equaled distant from the Target Day in absolute value, the later visit should be used.

Observations on the actual day will be used to analyze Days 2-15 Pruritus NRS. Weeks 2, 4, 8 and 12 Pruritus NRS will be based on the windowing method.

Safety analysis will follow CaPS.

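### Week 2 itch response uses the entry closest to Day 15 within Days 2-22, mapped before the dropout rule, so an early dropout with a responding entry can count as a Week 2 responder

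*SAP*

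**What the plan says.** The key secondary endpoint in SAP 3.2.1 is a response of at least 4 points on the Peak Pruritus "Numerical Rating Scale (NRS) from baseline at Weeks 2, 4, and 12". SAP 5.1 gives the Week 2 hypothesis its place in the testing order: "200 mg QD vs placebo at Week 2 will be assessed at the 2.5% level", directly after the 200 mg co-primaries. If it is rejected, Sequence A is tested at 5%; if not, at 2.5%.

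SAP Appendix 2 has two rules for the itch score. For the daily analyses: "Observations on the actual day will be used to analyze Days 2-15 Pruritus NRS". For the visit-labelled analyses: "Weeks 2, 4, 8 and 12 Pruritus NRS will be based on the windowing method". The Week 2 window has target Day 15 and runs from Day 2 to Day 22. Within a window the rule is: "If two or more visits fall into the same window, keep the one closest to the Target Day", with the later one used in a tie. No maximum distance from the target is set.

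Day 15 itself is analysed by actual day. SAP 6.2.3.1 lists "PP-NRS4 Response each day from Days 2-15 and Week 8". SAP 6.2.3.3 lists "Percent Change from Baseline in PP-NRS from Days 2-15, Weeks 4, 8 and 12", with no separate windowed Week 2.

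On missing data, SAP 5.3.1 first maps observed data to nominal visits. It then makes dropouts non-responders at visits after the last observed value, and leaves intermittent gaps in other participants missing. Protocol 9.4.2.2 says of binary secondary endpoints: "So missing responses would be defined as" non-response. SAP 2.1.1 makes dropouts non-responsive after that point, protocol 9.1.1 counts anyone who discontinues study treatment as a non-responder, and protocol 9.4.2.1 does the same for endpoints after withdrawal from the study.

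**The concern.** The order of operations matters. Because mapping comes first, an entry made in the first days of treatment can be relabelled as the Week 2 value. The dropout rule then starts only at the next visit. A participant who stops on, say, Day 5 after a responding entry, with nothing recorded on Days 6-22, is a Week 2 responder although they had left ten days before the target day. Under the composite estimand that participant should be a non-responder at Week 2.

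This falls on a tested hypothesis that also sets the significance level for Sequence A. It need not be neutral between arms: protocol 2.2.2 reports that the itch score separated from placebo as early as 2 days after starting 200 mg.

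**Working it through.** **The plan's own figure.** No power is stated for Week 2 itch response, so there is no figure to reproduce on this point. The co-primary power statements (75 per arm, two-sided 5%) do reproduce: Fisher's exact test gives 80.7% for IGA (12% versus 32%) and 96.1% for EASI-75 (23% versus 53%), against the stated 80% and 96%.

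**Window arithmetic (SAP Appendix 2).**
- Earliest offset: 15 - 2 = 13 days before target.
- Latest offset: 22 - 15 = 7 days after target.
- Width: 22 - 2 + 1 = 21 days.
- Protocol Week 2 visit window: ±1 day. This is read from the extracted schedule row (None, None, ±1, ±1, ±2, ±3, ±3, ±3, ±3), taking the nine entries as Visits 1 to 9 and Week 2 as Visit 4.

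**When an early value stands, under the closest-to-target rule.**
- Day 15 recorded: Day 15 is used, and Week 2 equals the actual-day Day 15 result.
- Day 8 value: only if there is no entry on Days 9-22 (Day 22 ties and wins as the later).
- Day 5 value: only if there is no entry on Days 6-22.
- Day 2 value: only if there is no entry on Days 3-22.

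**Effect of early dropouts.** Inputs are 75 per arm (SAP 2.2) and the Phase 2b Day 15 response rates of 69.8%, 41.1% and 15.7% for 200 mg, 100 mg and placebo (protocol 2.2.2). The share of early dropouts is not in the documents; 2%, 4% and 6% of each arm are assumed. It is also assumed that their last early entry responds at the Phase 2b Day 15 rates.
- One participant: 1/75 = 1.33 points.
- Shift in difference = share × (active rate - placebo rate).
- 200 mg: 0.02, 0.04, 0.06 × (0.698 - 0.157) = 1.1, 2.2, 3.2 points.
- 100 mg: 0.02, 0.04, 0.06 × (0.411 - 0.157) = 0.5, 1.0, 1.5 points.
- Wider assumed range for an active arm (2-10% early dropout, 20-70% early response, placebo early response 5%): from 0.02 × (0.20 - 0.05) = 0.3 to 0.10 × (0.70 - 0.05) = 6.5 points.

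**Effect of in-study diary gaps.** SAP 5.3.1 would otherwise leave these values missing. If their early response equals the Day 15 rate of their arm, including or excluding them does not move the expected difference. A shift like the one above appears only if gaps are scored as non-response, as in protocol 9.4.2.2.

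**Could it change the test?**
- At Phase 2b rates, power for 200 mg with 75 per arm is above 99.9% at 2.5% (pooled normal formula), so no.
- In a much closer result it could. In a hypothetical unstratified pooled z-test, 24/75 versus 12/75 gives p = 0.022, which passes 2.5%; 23/75 versus 12/75 gives p = 0.034, which does not.

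**The case against.** The best defence is that contiguous, prespecified windows with a nearest-day rule are a legitimate choice. A reader might infer from the Days 2-22 window that any diary day can serve as Week 2. The documents do not support that: there is no free choice of day, and a participant with a Day 15 entry gets the same value in both analyses. This stands, and confines the point to people without entries near Day 15. The rule is, however, worded for visits rather than diary entries, and it sets no distance limit.

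A reader might also infer that the window inflates the treatment difference in general. That is not shown. For a participant still in the study, the SAP alternative is a missing value, not non-response. If itch response builds over two weeks, early values could shrink the difference. The early-onset statement concerns the mean itch score at 200 mg, not the 4-point response, and not 100 mg. The protocol-SAP difference on intermittent gaps is a separate matter to reconcile.

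The remaining case is the early dropout. One can say that this is an ordering fault in SAP 5.3.1 rather than a windowing fault. It is both: the ordering lets the value through, and the window decides how early that value may be.

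**Conclusion.** Wrong as written, with low materiality. The Week 2 rule and the mapping order together can score an early dropout as a Week 2 responder, contrary to the composite estimand in protocol 9.1.1 and SAP 2.1.1, on the hypothesis that sets the level for Sequence A.

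The size depends on how many participants drop out early after a responding entry, which the documents do not give. The 1.1-3.2 point figure for 200 mg rests on the assumed 2-6% share and on early response at Phase 2b Day 15 rates; early dropouts may respond less often. No bias is claimed for in-study diary gaps.

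Two limits on what can be seen: the order of Sequence A is in a figure that is not shown, and the schedule row for the itch score is broken in the extracted text, so it cannot be confirmed whether daily entries continue on Days 16-22.

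**What to change.** - **SAP Appendix 2:** define Week 2 PP-NRS as the Day 15 diary value or, if that is missing, the nearest diary value within the protocol's Week 2 visit window (read as ±1 day; confirm against the original schedule).
- **SAP 5.3.1:** state that dropout non-response is applied by date before windowing, so that a participant who dropped out before that window is a non-responder at Week 2. Name the date used, since protocol 9.1.1 speaks of stopping treatment and SAP 2.1.1 of dropping out.
- **In-study diary gaps:** use the same missing-data rule as for Weeks 4 and 12, after reconciling SAP 5.3.1 (left missing) with protocol 9.4.2.2 (non-response). Narrowing the window alone would not settle this.
- **Sensitivity analysis:** keep the Days 2-22 version.

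The cost is a sentence or two in the SAP and a small programming change before unblinding, using diary data already planned. The downside is that a few participants become non-responders or missing, so Week 2 response rates or the number analysed may fall slightly.

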Appendix 3. A Logistic-normal GLMM for Longitudinal Binary Data and Tipping Point Analysis

Let Y_{ij} be the binary outcome for subject i ($i = 1, 2, \dots, N$) and visit j ($j = 1, 2, 3, 4$). We assume $Y_{ij} = 1$ for a response and $Y_{ij} = 0$ for a non-response. Then we model as:

$$P(Y_{ij} = 1 | x_{ij}, u_i) = \frac{e^{\beta' x_{ij} + u_i}}{1 + e^{\beta' x_{ij} + u_i}} \equiv \pi_{ij}(\beta; u_i)$$

Here, β is a vector of unknown parameters corresponding to the vector of fixed effects x_{ij} and u_i is a subject-specific random effect which is assumed to be normally distributed with mean 0 and variance σ^2 . Note that conditional on u_i , Y_{ij} is independent of Y_{ik} , when $j \neq k$.

The full marginal likelihood of the data is then,

$$L(\beta, \sigma^2) = \prod_{i=1}^N \int_{-\infty}^{\infty} \prod_{j=1}^4 \pi_{ij}(\beta; u_i)^{Y_{ij}} (1 - \pi_{ij}(\beta; u_i))^{(1-Y_{ij})} \times N(u_i; 0, \sigma^2) du_i$$

There is no closed analytical form for this likelihood.

For the present study, the primary endpoint is evaluated at Visit 8 / Week 12 ($j = 4$). There are three treatment groups, so the model term $\beta' x_{ij}$ when written out looks like,

$$\beta_0 + \sum_{k=1}^3 \beta_{1k} \times 1_{(T_i=k)} + \beta_{2j} + \sum_{k=1}^3 \beta_{3jk} \times 1_{(T_i=k)}$$

Here, T_i represents treatment for subject i . The third term in the expression is the effect for visit j and the fourth term in the expression is the interaction effect between treatment and visit. With an overall intercept term, the model is over-parameterized as written and so to fit the model, some restrictions on β are required. The default option (this can be changed using programming syntax) in standard statistical software is to assume $\beta_{13} = 0, \beta_{24} = 0$, thereby interpreting β_{11}, β_{12} as the difference in treatment effect relative to $T = 3$ and $\beta_{21}, \beta_{22}, \beta_{23}$ as the difference in visit effect relative to $V = 4$. Consequently, $\beta_{3jk} = 0$ when $j = 4$ or $k = 3$. So, for example, for a subject taking PF-04965842 100 mg QD at Week 12, the expression would be $\beta_0 + \beta_{11}$. For a subject taking PF-04965842 200 mg QD at Week 12, the expression would be $\beta_0 + \beta_{12}$. For a subject on placebo at Week 12, the expression would be β_0 .

Tipping Point Analysis

A method to analyze the longitudinal data of a binary endpoint measured during the placebo-controlled period (eg, IGA and EASI-75 response rates at Weeks 2, 4, 8 and 12) under the MNAR assumption is called the tipping point analysis. This tipping point analysis includes two popular scenarios as special cases: (1) the Jump-to-Reference (JTR) analysis in which the response rate for a missing subject assessment in the active treatment group takes

090177e19618b8f5\Approved\Approved On: 25-Jan-2021 08:47 (GMT)

on (ie, jumps to) the rate for the reference or control treatment group and (2) the MAR analysis in which the response rate for a missing subject assessment in each treatment group is based on the posterior predictive response rate for that treatment group alone.

The saturated logit normal GLMM as described above will be used as the imputation model. Estimation of the model parameters will be performed under the Bayesian framework using Markov Chain Monte Carlo (MCMC) methods. We assign a non-informative prior for each component of β to be independent and identically distributed as $\sim N(0, 10000)$ and assign a weakly informative prior for σ^2 as an Inverse-Gamma distribution with shape=1 and scale=1. With this prior distribution, the 90th percentile for σ^2 is approximately 9.

Let $\beta^b, u_i^b, b = 1, 2, \dots, B$ be a sample from the posterior distribution. A single imputation $\widetilde{Y}_{i,j}^b$ of missing Y_{ij} is based on the posterior predictive distribution of the response probabilities estimated from the GLMM. For example, if subject i is randomized to PF-04965842 100 mg QD ($T_i = 1$), then at Week 12 ($V = 4$),

$$\text{logit}(\pi_{i,1,4}^b) = \text{logit} \left(P(\widetilde{Y}_{i,4}^b = 1 | T_i = 1, V = 4) \right) = \beta_0^b + \beta_{11}^b + u_i^b.$$

If subject i is randomized to PF-04965842 200 mg QD ($T_i = 2$), then at Week 12 ($V = 4$),

$$\text{logit}(\pi_{i,2,4}^b) = \text{logit} \left(P(\widetilde{Y}_{i,4}^b = 1 | T_i = 2, V = 4) \right) = \beta_0^b + \beta_{12}^b + u_i^b.$$

If subject i is randomized to placebo ($T_i = 3$), then at Week 12 ($V = 4$),

$$\text{logit}(\pi_{i,3,4}^b) = \text{logit} \left(P(\widetilde{Y}_{i,4}^b = 1 | T_i = 3, V = 4) \right) = \beta_0^b + u_i^b.$$

In the tipping analysis, we apply a series of fixed quantities $\delta = (\delta_1, \delta_2)'$ to account for MNAR. We define,

$$\begin{aligned} \pi_{i,3,4}^{*b} &= \pi_{i,3,4}^b, \\ \pi_{i,1,4}^{*b} &= \delta_1 \pi_{i,3,4}^b + (1 - \delta_1) \pi_{i,1,4}^b, \\ \pi_{i,2,4}^{*b} &= \delta_2 \pi_{i,3,4}^b + (1 - \delta_2) \pi_{i,2,4}^b \end{aligned}$$

We then sample the single imputed value $\widetilde{Y}_{i,j}^b$ from a Bernoulli distribution with probability of success $\pi_{i,T_i,4}^{*b}$. For the present analysis, the responses from the placebo arm are not shifted.

Analysis of an imputed data set will produce an estimate as well as standard error of the treatment difference using CMH and normal approximation in Section 5.2.1. For a given value of MNAR parameter δ , this is repeated for B (typically, $B=500$) times to generate B complete imputed data sets and these B sets of estimates are combined using the Rubin's Method (Rubin, 1987).⁴ This can then be repeated for different values of MNAR parameter δ to evaluate the impact of missing data. Note that $\delta = (0, 0)'$ corresponds to an

MAR analysis and $\delta = (1, 1)'$ corresponds to an analysis commonly known as Jump-To-Reference (JTR). As a special case, we will consider $\delta_1 = \delta_2$ for our analyses.

090177e19618b8f5\Approved\Approved On: 25-Jan-2021 08:47 (GMT)

Appendix 4. Investigators Global Assessment

The clinical evaluator of atopic dermatitis will perform an assessment of the overall severity of atopic dermatitis and assign an IGA score and category as described in the table below. The assessment will be a static evaluation without regard to the score at a previous visit.

IGA Score

Score	Category	Description*
0	Clear	Atopic dermatitis is cleared, except for any residual discoloration (post-inflammatory hyperpigmentation and/or hypopigmentation).
1	Almost Clear	Overall, the atopic dermatitis is not entirely cleared and remaining lesions are light pink (not including post inflammatory hyperpigmentation) and/or; have barely palpable hard thickened skin and/or papules and/or; have barely perceptible lichenification; excoriation and oozing/crusting are absent.
2	Mild	Overall, the atopic dermatitis consists of lesions that are light red; with slight, but definite hard thickened skin and/or papules; with slight, but definite linear or picked scratch marks or penetrating surface injury; with slight, but definite thickened skin, fine skin markings, and lichenoid scale; oozing/crusting is absent.
3	Moderate	Overall, the atopic dermatitis consists of lesions that are red; with easily palpable moderate hard thickened skin and/or papules; with moderate linear or picked scratch marks or penetrating surface injury; with moderate thickened skin, coarse skin markings, and coarse lichenoid scale; with slight oozing/crusting.
4	Severe	Overall, the atopic dermatitis consists of lesions that are deep, dark red; with severe hard thickened skin and/or papules; with severe linear or picked scratch marks or penetrating surface injury; with severe thickened skin with very coarse skin markings and lichenoid scale; with moderate to severe oozing/crusting.

* The IGA will exclude scalp, palms, and soles from the assessment/scoring.

